8.4. Methods and Procedure

If a technical malfunction of the ARES was to occur, a conventional bronchoscope will be used at the discretion of the investigator. The study procedure may be recorded with an external video camera for educational purposes only.

Bronchoscopy:

Sedation: General anesthesia will be administered by an anesthesiologist per standard care at El Camino Hospital in a dedicated bronchoscopy suite. Patients will be continuously monitored throughout the procedure as per standards practices at El Camino Hospital.

Airway inspection: When adequate sedation has been given, the bronchoscope (BF-P190, Olympus, Tokyo, Japan) will be inserted into the tracheobronchial tree through endotracheal tube and a standard airway inspection will be performed.

Robot-assisted bronchoscopy: Following standard airway inspection, the robotic system will be positioned in an operative position. A study investigator will connect the sterile robotic bronchoscope to the light source and camera box, manually inserted the bronchoscope into the endotracheal tube and attached it to the robot. Then, the investigator will remotely advance the bronchoscope into the bronchial tree using the endoscope controller and will navigate it into the targeted lobar segment using EM navigation. In addition to direct visualization, monoplanar fluoroscopy may be used to provide additional viewing method during all procedures.

CONFIDENTIAL

REBUS: Once the bronchoscope was positioned within 2 cm from the targeted lesion, REBUS probe will be passed to confirm localization of a targeted lesions. The REBUS images will be recorded and classified as either concentric or eccentric.

TBNA and Biopsy: An aspiration needle will be first inserted into the working channel and advanced along the same pathway to the lesion. Four needle aspirations will be performed from the targeted lesion. Secondly, four biopsies will be performed using forceps and acquired samples will be placed in formalin.

ROSE: Needle aspiration samples will be plated on slides for immediate on-site evaluation by the cytopathology team, as per the standard practice of the Interventional Pulmonology team at El Camino Hospital. Rapid on-site evaluation (ROSE) of acquired cytologic specimen will be performed in all cases.

ROSE diagnostic: If ROSE provides a definitive diagnosis, the procedure will be completed.

ROSE non-diagnostic: If ROSE does not provide a definitive diagnosis, conventional bronchoscopy will be performed.

Conventional Bronchoscopy: In cases in which ROSE using a robotic bronchoscope does not provide a definitive diagnosis, a conventional bronchoscopy using standard EM navigation may be used.

8.5. Post Bronchoscopy

Prior to hospital discharge, all subjects will be evaluated for adverse events. These data will be captured in the Case Report Forms. The patient will be managed post-operative in a dedicated post-procedure area as per standard practices at El Camino Hospital. The subject will be monitored for postoperative symptoms and will undergo a chest X-ray within 2 hours from the conclusion of the procedure, to rule out complications such as pneumothorax. Prior to hospital discharge, the investigator and/or designee will arrange a follow-up appointment.

8.6. Follow-up

The subject will have a follow-up phone call on day 1 post procedure (24 hours \pm 12 hours), a follow-up appointment in the clinic 7 days post-procedure \pm 3 day and the final phone call follow-up 6 weeks \pm 7 days post-procedure.

8.7. Study Exit

Once the subject has completed 6 weeks follow-up or has withdrawn, they should be exited from the Study provided they do not have any conditions that require continued follow-up. The date of exit and subject status will be recorded on the Study Completion Form.

9. Assessment of Device Performance

9.1. Primary Effectiveness Endpoint

The primary effectiveness endpoint is the completion of the intended bronchoscopic procedure as defined by the ability to acquire tissue with biopsy tools.

Ability to acquire tissue with biopsy tools: The sum of ARES results that were positive for tissue acquisition divided by the sum of all targets.

9.2. Secondary Effectiveness Endpoints

The following will be considered secondary endpoints:

- Identification of correct bronchi leading to the targeted lesions
- Ability to localize targeted lesion
- Alignment capabilities
- Time to REBUS confirmation (lesion localization), time to the tissue acquisition confirmation, Total procedure time (from introduction to removal of the bronchoscope) and procedure interruptions
- Diagnostic yield
- Conversion to conventional bronchoscopic procedure
- Anesthesia time

Identification of correct bronchi leading to the targeted lesions: The principal investigator will assess the capabilities of the ARES navigation to identify optimal path to the targeted lesion.

Ability to localize targeted lesion: Radial probe endobronchial ultrasound will be used in all cases to confirm the presence of a lesion immediately before performing biopsy.

Alignment capabilities: The sum of ARES results that were positive for the first attempt of tissue acquisition divided by the sum of all attempts.

Time to REBUS confirmation: Is defined by the time the ARES bronchoscope is inserted into the oropharynx until the localization of the targeted lesion is confirmed by REBUS.

Time to the tissue acquisition confirmation: Is defined by the time the ARES bronchoscope is inserted into the oropharynx until the tissue acquisition is confirmed by the ROSE.

Total procedure time: Total procedure time is defined by the time the ARES bronchoscope is inserted into the oropharynx until the time a biopsy tool is removed.

Diagnostic yield: $=\frac{a+b}{n}$ where

- a = the sum of ARES results that were diagnostically positive for malignancy at 6-week follow-up
- b = the sum of the ARES results that were diagnostically negative for malignancy at 6-week follow-up
- n = the sum of all targets

Conversion to conventional bronchoscopic procedure: If ROSE does not provide a definitive diagnosis in 4 attempts, the conventional bronchoscopy will be used to acquire additional specimens.

Number of the procedure converted to the conventional bronchoscopy for any reason.

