We, the undersigned, have read and approve the protocol specified above and agree on its content.

CONFIDENTIAL October 5, 2017

ARES study – Investigator's Signature Page

STUDY TITLE: Auris Robotic Endoscopy System (ARES) for Bronchoscopy – NSR Study

A SINGLE-CENTER, PROSPECTIVE, SINGLE ARM STUDY TO EVALUATE THE PERFORMANCE OF THE AURIS ROBOTIC ENDOSCOPY SYSTEM (ARES) FOR BRONCHOSCOPIC PROCEDURES

STUDY CENTER:

I, the undersigned, have read and understand the protocol specified above and agree on its content. I agree to perform and conduct the study as described in the protocol. In addition, when applicable, I agree to enlist sub-investigators who also agree to perform and conduct the study as described in the protocol.

DATE

Protocol Synopsis

Auris Robotic Endoscopy System (ARES) for Bronchoscopy – NSR Study

A SINGLE-CENTER, PROSPECTIVE, SINGLE ARM STUDY TO EVALUATE THE PERFORMANCE OF THE AURIS ROBOTIC ENDOSCOPY SYSTEM (ARES) FOR BRONCHOSCOPIC PROCEDURES

Primary Objective	The objective of this study is to evaluate the performance of the novel Auris Robotic Endoscopy System (ARES) during bronchoscopy procedures. Product features may be added and/or revised during the conduct of the study and will be evaluated by the physician. Appropriate notifications to Institutional Review Board (IRB) will be made of any revisions. The study is a Non-Significant Risk (NSR) feasibility study with no specific statistical study size or power.
Test Device	Monarch Robotic Endoscopy Platform, the next generation of Auris Robotic Endoscopy System (ARES)
Control Device	None
Indication for Use 510K #: K152319	The previous ARES is FDA cleared medical device (510K #: K152319) intended to provide bronchoscopic visualization of patient airways. The Auris Robotic Endoscopy System (ARES) is intended to be used by qualified physicians to provide visualization to the bronchial tree during bronchoscopic procedures. The Monarch Robotic Endoscopy Platform (Monarch Platform) and its accessories are intended to provide bronchoscopic visualization of and access to patient airways for diagnostic and therapeutic procedures.
	access to patient an ways for diagnostic and therapeutic procedures.
Hypotheses	No formal statistical hypotheses are defined. It is believed that the Auris system will be capable of enhancing access to peripheral lung lesions.

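### Section 9.2 divides first-attempt successes by all attempts, so the alignment score is not a first-attempt success rate; counting every scheduled pass caps it at 25%, or 12.5% on a less supported reading (minor, endpoint definition)

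*Protocol*

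**What the plan says.** Section 9.2 gives the formula for alignment capabilities: "The sum of ARES results that were positive for the first attempt of tissue acquisition divided by the sum of all attempts". The synopsis only lists the item, so this is its sole definition in the protocol.

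Three other places bear on how it should be read.

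- Section 8.4 sets the sampling sequence per lesion: "Four needle aspirations will be performed from the targeted lesion. Secondly, four biopsies will be performed using forceps". Rapid on-site evaluation (ROSE) is applied to the needle samples; the forceps samples go to formalin.
- Section 9.2, on conversion to conventional bronchoscopy, uses the word attempts for repeated tries: "If ROSE does not provide a definitive diagnosis in 4 attempts".
- Where the protocol means targets, it says so. The primary endpoint in 9.1 is "The sum of ARES results that were positive for tissue acquisition divided by the sum of all targets", and diagnostic yield in 9.2 has "n = the sum of all targets".

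No section defines an attempt, says which pass is the first, or equates attempts with first attempts or with targets.

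**The concern.** A proportion restricted to first attempts above the line needs the same restriction below it. Here the numerator can count at most one success per target (or one per tool), while the denominator, taken at its word, grows with every later pass. The result is not the share of first attempts that succeeded.

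What is at stake is how one performance figure is read. Followed literally, flawless alignment would be reported as a low percentage beside a primary endpoint and a diagnostic yield that are both per target and can both reach 100%. Two analysts with the same data could also report different figures, depending on which passes they counted.

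**Working it through.** **Inputs.** Four needle passes and four forceps passes per lesion (8.4). Up to 60 patients (5.2). One target per patient is an assumption for illustration; the number of targets cancels from the ratio when pass counts are equal. The protocol states no expected value for this endpoint, so there is no figure to reproduce.

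**Formula.** Let p be the true first-attempt success rate and k the number of counted passes per target. With one first attempt per target the score is (60 × p)/(60 × k) = p/k. With a separate first attempt for each of two tools and eight passes it is 2p/8 = p/4.

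**Every scheduled pass counted.**

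| Reading of attempts | p = 100% | p = 90% |
|---|---|---|
| Needle passes only, k = 4 | 60/240 = 25% | 54/240 = 22.5% |
| Both tools, one first attempt per tool | 120/480 = 25% | 108/480 = 22.5% |
| Both tools, one first attempt per target, k = 8 | 60/480 = 12.5% | 54/480 = 11.25% |

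The first row has the best textual support. The only numbered use of attempts in 9.2 is four, tied to ROSE, and 8.4 applies ROSE to needle samples. The third row needs forceps passes below the line but no forceps first attempt above it. It stays possible because 9.1 speaks of biopsy tools without limiting them to the needle.

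**Reading backwards.** A reported 10% means p = 0.10 × 4 = 40% at k = 4 (24/240), but p = 0.10 × 8 = 80% at k = 8 (48/480).

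**Passes counted only up to the first success.** At p = 100% the score is 60/60 = 100%. If 54 targets succeed on pass one and 6 on pass two, the denominator is 54 × 1 + 6 × 2 = 66 and the score is 54/66 = 81.8%. The first-attempt rate is 54/60 = 90%.

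**First attempts as denominator.** If all 60 targets have a first attempt, p = 100% reads 60/60 = 100% and p = 90% reads 54/60 = 90%.

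**The case against.** **The low ceilings depend on one reading.** This stands. The 25% and 12.5% figures require every scheduled pass to count. Counting passes up to the first success is a coherent measure with a ceiling of 100%. The protocol does not state that reading, however, and it still does not return the first-attempt rate.

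**The endpoint is never called a first-attempt success rate.** True: its label is alignment capabilities, and the target quantity is inferred from the numerator. The inference is natural, but it is an inference.

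**The harm is small.** This also stands. The synopsis says "No formal statistical hypotheses are defined", no threshold is attached to this item, and with equal pass counts the score is p rescaled, so ordering is kept. If the first-attempt outcome is recorded per target, the rate can be recalculated later. The case report forms are not in the document, so that cannot be confirmed.

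**A stronger reading to resist.** A reader might infer that the score is also distorted by how intensively each target was sampled. With unequal pass counts it would be: 60/60 first-attempt successes at eight passes score 60/480 = 12.5%, below 36/60 at four passes, 36/240 = 15%. Section 8.4 might seem to allow unequal counts: "If ROSE provides a definitive diagnosis, the procedure will be completed", and "If a technical malfunction of the ARES was to occur, a conventional bronchoscope will be used at the discretion of the investigator". But the text does not settle whether either event shortens the sequence, and the same section schedules four aspirations and four biopsies. The distortion is therefore conditional and not established.

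**Conclusion.** The definition is wrong as written, and the matter is minor. Numerator and denominator do not match on the protocol's own use of the word attempts. Only reading the denominator as all first attempts, or as all targets where every target has one, yields a first-attempt rate, and no section says either.

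The size depends on the reading. With every scheduled pass counted, perfect success is reported as 25% (best supported) or 12.5% (less supported). With passes counted up to the first success, the ceiling is 100%, but the example gives 81.8% against 90%. The figures assume 60 single-target patients and, for the 25% and 12.5% ceilings, the full 8.4 sequence.

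A reader might take this to mean that the device's performance cannot be judged from the study. The document does not support that: the fault is limited to one descriptive secondary endpoint, and the primary and safety endpoints do not use this formula. Nor does the protocol state a wrong number; this is a fault of endpoint definition.

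**What to change.** Restate the endpoint in 9.2 as: *number of targets with tissue acquired on the first ARES attempt, divided by the number of targets with a first ARES attempt*. Add a note saying which pass is the first attempt, and whether each tool has its own.

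If the sponsor prefers all targets as the denominator, to match 9.1 and diagnostic yield, it should state that choice and its consequence: a target never sampled with the device then counts as an alignment failure, which mixes navigation or device failure into the measure. For illustration, if 54 of 60 targets had a successful first attempt and the other 6 were never sampled, the result is 54/54 = 100% on first attempts and 54/60 = 90% on all targets.

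Report the counts with the percentage. If a per-pass success rate is wanted, report successful attempts over all attempts separately.

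The cost is one sentence of protocol wording and a short note. The current numerator already needs the first-attempt outcome for each target; the sponsor should check that the case report forms capture it. No study procedure changes.

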Preliminary qualification (Inclusion/Exclusion criteria). Principal Investigator is responsible for certifying that key personnel have received adequate training to ensure they are aware of the regulations governing human subjects research and understand and adhere to the IRB-approved research protocol. Compliance with these standards provides assurance that the rights, safety, and well-being of human subjects are protected and the integrity of the data collected. Potential study candidates must meet the study specific Inclusion/Exclusion criteria based on the screening assessment. For the purpose of this study, a peripheral lung lesion is defined as a lesion located in a sub segmental branch of the bronchial tree that it cannot be accessed by convex probe endobronchial ultrasound.

Medical history. During the screening/baseline assessment, the investigator or coordinator will record details of medical history as they relate to pulmonary status.

Physical examination. The investigator will perform a brief, directed physical and pulmonary examination and document any preoperative abnormalities. The examination will be repeated at the day 7 post-procedure.

Electrocardiogram (ECG). Stickers will be placed on each arm and leg and to your chest area and a heart tracing is performed to measure electrical activity of your heart.

Blood tests including the PT/INR coagulation test. These tests may be needed before the procedure to ensure that study patients have no problems related to blood clotting. (see above). Bleeding can sometimes occur after bronchoscopy, especially if tissue samples are taken. The study patients will be asked to stop anticoagulants several days prior to the procedure (see Table 1. above).

HRCT scan. CT analysis will require a full inspiratory CT scan. CT Scans should be performed no longer than 30 days pre-procedure as part of screening assessment. Specific CT parameters for scanner model and manufacturer will be provided to the site. De-identified CT scans may be provided to the study sponsor.

Fluoroscopy. Fluoroscopy will be used in conjunction with the bronchoscopy to provide an additional viewing method during the procedure.

Radial probe endobronchial ultrasound (REBUS). REBUS will be used to confirm the presence of a lesion in patients where additional confirmation may be needed.

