Chest X-ray. Patients will undergo a routine chest X-ray within 2 hours from the conclusion of the procedure to o rule out complications such as pneumothorax.

Concomitant Medications. Principal investigator will determine relevant disease/procedure specific concomitant medications that is important for a study conduct. Only the relevant medication will be recorded on a rolling medication log or the relevant case report forms.

Follow-up. The 24 hours (\pm 12 hours) follow-up will be a phone consultation, 7 days (\pm 3 days) follow-up will be an office visit and 6 weeks ((\pm 1 week) follow-up will be a phone consultation. During the follow-up, adverse events will be recorded and associated case report forms will be completed.

Navigation/Control evaluation. The system navigation/control will be evaluated and recorded on the procedure CRFs.

Biopsy sample evaluation. Content and adequacy of biopsy samples will be assessed by pathologist or cytotechnologists using the rapid on-site evaluation (ROSE). A preliminary diagnosis will be recorded. The final histopathologic diagnosis will be recorded on the week 6 follow-up CRF.

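### Diagnostic yield counts a negative ARES result as a success without requiring a benign diagnosis that explains the lesion, and without a rule for negatives that other tissue contradicts

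*Protocol*

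**What the plan says.** Protocol section 9.2 gives the formula (a+b)/n. Here a counts ARES results positive for malignancy at week 6, n counts all targets, and "b = the sum of the ARES results that were diagnostically negative for malignancy at 6-week follow-up". The word *diagnostically* is not defined. Section 6.1.1 admits patients with solid peripheral lesions in which cancer is suspected.

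The tissue that could bear on b comes from three places:

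- Needle aspirates taken with ARES are read on site (ROSE, section 8.4). Under section 8.3, ROSE also judges whether the sample is adequate.
- Forceps samples taken with ARES are processed separately: "Secondly, four biopsies will be performed using forceps and acquired samples will be placed in formalin" (section 8.4).
- Conventional bronchoscopy can follow a ROSE that is not definitive.

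On the week-6 classification, section 8.3 says: "The final histopathologic diagnosis will be recorded on the week 6 follow-up CRF". It does not say which specimen that diagnosis comes from. The week-6 contact is a telephone call (sections 8.3 and 8.6). The only CT is the one before the procedure: "CT Scans should be performed no longer than 30 days pre-procedure as part of screening assessment". Section 8.7 delays exit for conditions that need more follow-up, but b is tied to week 6.

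**The concern.** A yield should credit the device when its tissue settles what the lesion is. Here b is defined by the absence of malignancy in the result. Adequate tissue with only nonspecific change, or from beside the lesion, can be called negative without explaining what the CT showed. In a population selected for suspected cancer, some of those negatives will plausibly be missed cancers. The formula would then count the miss as a success.

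The qualifier about week 6 names a time and not a reference standard. No repeat imaging or tissue is scheduled that would test a negative by then, and no rule says what happens when other tissue disagrees with it.

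What is at stake is the meaning of one descriptive figure. Section 4 says the results may guide product development, and section 17 allows their publication or submission to regulators. A reader of the reported yield could not tell how much of it is cancer found, benign disease identified, or negatives that nobody checked.

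**Working it through.** **No figure to reproduce.** The protocol states no expected yield, power or precision, and section 10 contains no statistical plan. The check therefore works from the formula in section 9.2.

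**Step 1: which results can enter b.** There are two readings. Reading A: the label given to the ARES specimen stands. Reading B: b is the status at week 6, after final histology.

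| Target | Reading A | Reading B | With the fix |
|---|---|---|---|
| 1. Specific benign diagnosis from ARES tissue, uncontradicted | in b | in b | in b |
| 2. Adequate but nonspecific ARES tissue, lesion benign | can be in b | can be in b | non-diagnostic |
| 3. Adequate but nonspecific ARES tissue, lesion malignant, nothing contradicts it by week 6 | can be in b | can be in b | non-diagnostic |
| 4. ARES tissue negative, other tissue malignant by week 6 | in b | not in b | non-diagnostic |
| 5. Inadequate ARES sample | out only if *diagnostically* excludes it | same | non-diagnostic |

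The readings differ only in row 4. That row needs a particular path: ROSE is not definitive, conventional bronchoscopy follows and its tissue is malignant, and the ARES forceps histology later reads negative. Row 3 is the problem that remains under both readings.

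**Step 2: the size per missed cancer.** Write b = t + m, with t true negatives and m missed cancers. Then

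(a + t + m)/n − (a + t)/n = m/n.

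Section 5.2 allows up to 60 patients. The number of targets per patient is not stated; one each is assumed.

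- m = 1: 1/60 = 1.67 points; 1/40 = 2.5 points; 1/20 = 5.0 points.
- At n = 60: m = 3 gives 3/60 = 5.0 points; m = 6 gives 6/60 = 10.0 points.

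**Step 3: why the total cannot be sized.** If tissue is obtained from every target, m/n = p(1 − s)k. Here p is the prevalence of malignancy, s is the share of malignant targets that ARES calls positive, and k is the share of missed cancers that are labelled negative and still in b at week 6. The protocol gives none of the three. As an assumption only, let p and s each lie between 0.6 and 0.8. Then p(1 − s) runs from 0.6 × 0.2 = 0.12 to 0.8 × 0.4 = 0.32, and:

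- k = 0: 0 points
- k = 0.25: 3 to 8 points
- k = 0.5: 6 to 16 points
- k = 1: 12 to 32 points

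A range of 0 to 32 points is not an estimate. It shows that the answer depends on k, which is the quantity the definition of b leaves open.

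**The case against.** The strongest reply is that b already means status at week 6. The formula says so, and section 8.3 has the final histology recorded at that time, so a target shown to be malignant by then is not negative at week 6. This stands as a natural reading. A reader might infer from the formula that a miss is credited even when conventional tissue from the same session shows cancer. The documents do not support that as their plain meaning. The path is also narrow, because diagnosis-driven conversion follows only a ROSE that was not definitive, and such a result is not obviously *diagnostically negative*.

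Further points that stand:

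- The protocol calls the quantity yield, never accuracy, and plans no comparison. The study has one arm and no formal hypothesis.
- The missing follow-up CT and the telephone contact show that negatives are not tested. They are not faults that the fix repairs, since it keeps the same cut-off.
- a and b are separate counts, so a/n could be reported without changing any definition.

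The reply does not reach row 3 of the table. A nonspecific negative that nothing has contradicted stays eligible for b on the week-6 reading too. Nor is this a detail left to the SAP, which was not available for this review: the protocol itself states the formula and what enters it.

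**Conclusion.** The concern holds in a limited form. As defined, b can credit nonspecific negatives that are uncontradicted by week 6, and the protocol does not say whether contradicted ones leave it. Each missed cancer that stays in b raises the yield by exactly 1/n, or 1.67 points at 60 targets under the assumption of one target per patient and full enrolment. The direction is certain only for misses that do stay in b. How many will do so cannot be derived from the protocol.

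One might go further and say that the yield reaches 100% whatever the sensitivity. That requires every target to give tissue called positive or negative, with *diagnostically* excluding nothing. Because adequacy is assessed, the documents do not support that reading.

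Impact is minor to moderate. The endpoint is one of several secondary ones, it is descriptive, and no error rate, power or decision rule depends on it. The change is still worth making because the definition is fixed in the protocol and is cheap to tighten.

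**What to change.** Reword section 9.2:

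- Define b as ARES-acquired specimens with a specific benign diagnosis that explains the lesion and is not contradicted by other tissue or diagnosis available by week 6, including tissue from any conventional bronchoscopy after conversion. Say who judges this.
- Count nonspecific, inadequate, atypical or contradicted results as non-diagnostic: kept in n, left out of a and b.
- Record the specimen source of the week-6 final diagnosis, if the CRF does not already do so. Without it, ARES tissue cannot be told apart from conventional tissue.
- Report a/n beside (a+b)/n.

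The cost is endpoint wording, some effort in classifying results, and probably one CRF field (the CRFs were not available to check). No visit or procedure is added. The reported yield will be lower, and some true negatives with only nonspecific histology will count as non-diagnostic. Contradiction can be detected mainly in converted targets, so checking will be uneven. A wrong but specific benign reading that nothing contradicts by week 6 will still count.

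Separately, the statements on conventional bronchoscopy after a non-definitive ROSE do not agree and must be reconciled. Section 8.4 says "If ROSE does not provide a definitive diagnosis, conventional bronchoscopy will be performed" and then that "a conventional bronchoscopy using standard EM navigation may be used", while section 9.2 says "the conventional bronchoscopy will be used to acquire additional specimens".
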